## 15. Secondary Endpoint Analyses

Reflection skills total score will be analyzed analogously to the primary endpoint. Retention of skills will be evaluated by comparing follow-up OSCE total scores between arms at the predefined time point using ANOVA or Kruskal-Wallis as appropriate.

## 16. Covariate-Adjusted Analyses (Exploratory)

If available, models may adjust for prespecified covariates such as prior academic performance, baseline checklist items, or attendance. Model diagnostics will be examined; if assumptions are violated, robust or nonparametric alternatives will be considered.

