## 1. Synopsis

- Design: Interventional, randomized, parallel-group, three-arm educational trial.
- Arms: (A) Digital interactive peer support; (B) Face-to-face peer support; (C) Standard training (control).
- Primary Endpoint: Objective Structured Clinical Examination (OSCE) total score immediately post-intervention (points; higher is better).
- Secondary Endpoints: Reflection skills scale total score immediately post-intervention; Retention assessed by a follow-up OSCE at a predefined interval (e.g., 8–12 weeks).
- Setting: Clinical Skills Laboratory within a Faculty of Medicine in Türkiye.
- Population: Adult medical students meeting eligibility criteria.
- Allocation: Approximately 1:1:1; no masking.
- Estimated/Actual Enrollment: About 100 participants (retrospective registration of a completed trial).

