## 5. Trial Design

Individually randomized, parallel assignment with three arms. Participants are assigned in approximately equal numbers to the digital, face-to-face, or standard training arms. Interventions occur within routine clinical skills teaching sessions. No masking is used.

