### Exclusion Criteria

- Prior formal certification or extensive training in the targeted clinical skills.
- Inability to attend scheduled peer-support sessions (digital or face-to-face).
- Conditions preventing participation in OSCE/assessment procedures.

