## 9. Procedures and Schedule

Following consent and baseline administrative checks, students receive instruction according to allocation. Outcome assessments include an immediate post-intervention OSCE and a validated reflection skills questionnaire. A follow-up OSCE is administered at a predefined interval (e.g., 8-12 weeks) to assess retention. Assessors use standardized checklists and instructions. No

investigational products are used.

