# Statistical Analysis Plan (SAP)

This SAP prespecifies analysis populations, endpoints, statistical tests, missing data handling, and multiplicity control. Analyses will be conducted using a two-sided significance level of 0.05.

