## 14. Primary Endpoint Analysis

Between-arm comparison of immediate post-intervention OSCE total scores: if assumptions are met, one-way ANOVA; otherwise, Kruskal-Wallis test. If the omnibus test is significant, perform pairwise comparisons with multiplicity adjustment (e.g., Bonferroni or Holm).

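### The primary OSCE comparison is valid but unadjusted: the starting-ability measures the SAP names sit in optional exploratory models, on an open list that includes post-allocation attendance, so precision is lost

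*Combined protocol and SAP*

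**What the plan says.** The primary endpoint (section 4) is a single OSCE total taken straight after the intervention, not a change from a starting value. Section 14 fixes its analysis: "Between-arm comparison of immediate post-intervention OSCE total scores: if assumptions are met, one-way ANOVA; otherwise, Kruskal-Wallis test". No covariate appears there, and section 15 carries the same approach over to the reflection score and the follow-up OSCE.

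Starting ability appears in the SAP only in section 16, whose heading marks it as exploratory: "If available, models may adjust for prespecified covariates such as prior academic performance, baseline checklist items, or attendance". The covariates are called prespecified, yet no closed list, model or decision rule is given.

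On what is recorded before teaching starts, section 9 says: "Following consent and baseline administrative checks, students receive instruction according to allocation". It mentions no skills test before instruction. Section 5 describes the allocation as "Individually randomized, parallel assignment with three arms" and mentions no stratification on ability. The exclusion criteria remove students with "Prior formal certification or extensive training in the targeted clinical skills", which leaves the ordinary spread of ability among those eligible.

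**The concern.** A score measured once, after teaching, reflects both what the teaching did and what the student brought to it. Students who start stronger will tend to score higher in any arm, and that variation sits in the error term of an unadjusted ANOVA. A measure of prior ability that predicts the OSCE would remove part of it, and would correct the estimate for whatever imbalance chance produced in this particular randomization. The SAP names such measures but does not commit to using them.

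Precision matters here because the trial is small, no sample-size calculation is given, and the pairwise comparisons carry a further multiplicity adjustment.

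The wording of section 16 adds two problems. Because adjustment is optional and the list is open, an analyst could decide after seeing results whether to adjust and for what. And attendance is listed alongside baseline variables although it happens after allocation. It may itself be affected by arm, and adjusting for it could remove part of the effect being estimated.

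**Working it through.** **Inputs from the documents.**
- Size: "Estimated/Actual Enrollment: About 100 participants (retrospective registration of a completed trial" (section 1).
- Ratio: "Allocation: Approximately 1:1:1; no masking" (section 1). This gives 100/3, taken as 33 per arm, 99 in all.
- Level: "Analyses will be conducted using a two-sided significance level of 0.05" (SAP introduction).

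The plan gives no power, target effect, OSCE SD or dropout rate, so there is no figure of its own to reproduce. Effects are therefore in SD units of the OSCE.

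**Assumptions.** Correlation r between the pre-allocation covariate and the OSCE: 0.3, 0.5 and 0.6. True benefit: 0.6 SD in both peer arms, arm means 0 / 0.6 / 0.6. Normal scores, no missing data.

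**1. Validity of the planned test.** Simulating the unadjusted ANOVA with no arm effect, r = 0.5 and 20,000 runs gave a rejection rate of 0.0498. The 5% level is kept.

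**2. Chance imbalance, and how much reaches the outcome.** The standard error of a difference between two arms in any baseline trait is √(2/33) = 0.246 SD. A given pair differs by more than 0.25 SD with probability 2 × [1 − Φ(0.25/0.246)] = 0.31. That is imbalance in the trait. Its expected contribution to the OSCE difference is r times as large: 0.25 × r = 0.075 / 0.125 / 0.15 SD at r = 0.3 / 0.5 / 0.6. Even an imbalance at the edge of the 95% range, 1.96 × 0.246 = 0.48 SD, carries about 0.14 / 0.24 / 0.29 SD.

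**3. Precision gained by ANCOVA.** Adjusted SE = 0.246 × √(1 − r²). Equivalent sample per arm = 33/(1 − r²). The 95% half-width is 1.96 × SE.

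**4. Omnibus power.** The arm means 0 / 0.6 / 0.6 average 0.4, so the squared deviations sum to 0.16 + 0.04 + 0.04 = 0.24. The noncentrality is λ = 33 × 0.24/(1 − r²) = 7.92/(1 − r²). The F test has 2 and 96 degrees of freedom, or 2 and 95 with one covariate.

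| r | SE (SD) | 95% half-width (SD) | Equivalent n per arm | λ | Omnibus power |
|---|---|---|---|---|---|
| unadjusted | 0.246 | 0.48 | 33 | 7.92 | 70% |
| 0.3 | 0.235 | 0.46 | 36 | 8.70 | 74% |
| 0.5 | 0.213 | 0.42 | 44 | 10.56 | 82% |
| 0.6 | 0.197 | 0.39 | 52 | 12.38 | 88% |

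With a smaller benefit of 0.5 SD in both peer arms, power rises from 53% to 57 / 66 / 74%.

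**The case against.** The strongest reply is that nothing is broken. Individual randomization is the main control on starting ability, and the unadjusted standard error already allows for chance imbalance. This stands. A reader might infer that a post-only comparison is biased or cannot tell teaching from prior ability; step 1 and the design do not support that.

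A reader might also take the 31% figure to mean that chance imbalance often rivals the teaching effect. It does not on these assumptions: a 0.25 SD imbalance contributes 0.075 to 0.15 SD to the OSCE difference, against an assumed effect of 0.6 SD, which is 4 to 8 times larger.

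Nor does the plan offer two rival primary answers. Section 14 sets the primary test and the heading of section 16 makes adjustment exploratory, so the hierarchy is clear. The open list weakens only the exploratory result.

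Sections 9 and 16 might be read as contradicting each other on baseline skill data. Section 16 is conditional on availability, and section 9 is a short narrative that does not claim to list every baseline item. That is an ambiguity to clear up, not a contradiction.

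Two practical objections also stand. The trial is described as completed, so replacing the primary analysis now could itself be a data-driven choice. And that the faculty holds a usable prior grade is an inference from section 16, not something the documents state.

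None of this removes the efficiency loss, and none of it answers the point about attendance.

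**Conclusion.** The point holds as a matter of precision and specification. The planned comparison is valid; it leaves chance imbalance uncorrected and gives up precision that a covariate the SAP itself names could recover. The gain is worth about 3, 11 or 19 extra students per arm (36, 44 or 52 against 33) at r = 0.3, 0.5 or 0.6. It is modest at 0.3 and material from 0.5 upward.

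The size rests on r, which the documents do not give, on 33 analysed students per arm, and on a usable pre-allocation measure existing. Two parts rest on none of these: the covariate list should be closed, and attendance does not belong on it.

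**What to change.** 1. In section 16, name one covariate fixed before allocation: prior academic performance, or baseline checklist items if they were recorded before allocation. Remove attendance from the list.
2. Analyse the immediate OSCE, the follow-up OSCE and the reflection score by ANCOVA on arm plus that covariate, with a simple stated rule for students whose covariate is missing.
3. Let the state of the data decide the order. If outcome data have not been seen, make the ANCOVA primary and keep ANOVA/Kruskal-Wallis as the supporting analysis. If they have been seen, keep the planned test as primary and report the ANCOVA beside it, labelled post hoc.
4. State in sections 9 and 16 whether baseline checklist items exist and when they were recorded; if they do not, delete them from section 16.
5. If no usable pre-allocation measure exists, say so and report it as a limitation. A baseline OSCE cannot be added to a completed trial.

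The cost is SAP wording, one more reported model per outcome and, if available, retrieval of a prior grade. The sponsor would need to confirm that the grade is held, is comparable across students and may be used under the consent given. A few students may lack one.

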## 17. Missing Data

Patterns of missingness will be described. Primary analyses will use available cases. Sensitivity analyses may include multiple imputation or nonparametric methods consistent with the primary analysis framework.

## 18. Multiplicity

For multiple pairwise comparisons following a significant omnibus test, p-values will be adjusted (e.g., Bonferroni/Holm) to control the family-wise error rate.

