## 2. Background and Rationale

Peer support is widely used in health professions education to promote practice, feedback, and reflection. Digital interactive platforms may expand access and flexibility compared with traditional face-to-face sessions. This study evaluates whether structured digital peer support is non-inferior or superior to face-to-face peer support, and whether either approach improves clinical skill performance compared with standard training.

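### Does leaving the pairwise adjustment open between Bonferroni and Holm, with no pairwise test named, call for a change to the plan?

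*Combined protocol and SAP*

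**What the plan says.** The opening of the SAP claims completeness: "This SAP prespecifies analysis populations, endpoints, statistical tests, missing data handling, and multiplicity control". It sets the level: "Analyses will be conducted using a two-sided significance level of 0.05".

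For the primary endpoint, Section 14 chooses the omnibus test by a check on the data: "if assumptions are met, one-way ANOVA; otherwise, Kruskal-Wallis test". A significant omnibus result leads to adjusted pairwise comparisons, with Bonferroni and Holm given as examples. Section 18 repeats this as a general rule: "For multiple pairwise comparisons following a significant omnibus test, p-values will be adjusted (e.g., Bonferroni/Holm) to control the family-wise error rate".

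Section 15 carries the approach to the reflection score: "Reflection skills total score will be analyzed analogously to the primary endpoint". For the follow-up OSCE it names only the omnibus test, so Section 18 governs any pairs compared there. No section says whether the pairs are tested with a pooled-SD t test, a Welch t test or a rank test.

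**The concern.** A plan that says it fixes the tests and the multiplicity control, and then gives two adjustments as examples, has not fixed them. The pairwise contrasts carry the trial's questions: Section 2 asks "whether either approach improves clinical skill performance compared with standard training" and also how digital compares with face-to-face support. Section 1 describes a completed trial registered retrospectively, so the method could in principle be chosen with the p-values in view. One permitted option, Bonferroni, is also never more powerful than the other on the same p-values.

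The unnamed test adds a second worry. If the SD is pooled over three arms whose SDs differ, the pairwise p-values may be wrong, and Holm then has less slack than Bonferroni to absorb the error. At stake would be a false claim about a pair, or a true difference missed because the weaker adjustment was used.

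**Working it through.** **Inputs.** Two-sided level 0.05 (SAP opening). Three arms, hence three pairs, in about equal numbers (Section 5). About 100 students (Section 1), taken as 33 per arm. The documents give no effect size or SD, so the effects and SDs below are assumptions.

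**1. The plan's own level.** Bonferroni tests each pair at 0.05/3 = 0.0167, and 3 × 0.0167 = 0.05. Holm compares the ordered p-values with 0.05/3 = 0.0167, 0.05/2 = 0.025 and 0.05. Both have family-wise level 0.05. The omnibus gate can only remove rejections.

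**2. The two can disagree.** Take pooled t values 2.628, 2.366 and 0.262 on 96 degrees of freedom.

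- Omnibus, equal arms: F = (2.628² + 2.366² + 0.262²)/3 = (6.906 + 5.598 + 0.069)/3 = 4.19, p = .018.
- Unadjusted p: .010, .020, .79.
- Bonferroni: 3 × .010 = .030; 3 × .020 = .060; 3 × .79, capped at 1.00. One pair is significant.
- Holm: 3 × .010 = .030; 2 × .020 = .040; 1 × .79 = .79. Two pairs are significant.

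**3. Choosing between them afterwards does no harm.** A pair that Bonferroni rejects has p ≤ 0.0167, which is no larger than any Holm threshold, so Holm rejects it as well. The pairs rejected by either method are therefore exactly the pairs rejected by Holm. An analyst who always took the more favourable answer would be running Holm, whose family-wise error is at most 0.05. In simulation (pooled t, equal SDs, F gate, 200,000 trials per setting) Holm's family-wise error was 4.2% with all means equal, 2.9% with both peer arms 0.6 SD above control, and 5.0% with one distant arm.

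**4. Size of the gain from fixing on Holm** (same simulation; both peer arms above control by the stated amount; Bonferroni versus Holm):

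| Effect | Power per pair versus control | Power to show both | Declared pairs differ |
|---|---|---|---|
| 0.4 SD | 21 vs 23% | 10 vs 13% | 3.8% of trials |
| 0.6 SD | 50 vs 53% | 34 vs 40% | 7.3% |
| 0.8 SD | 79 vs 82% | 68 vs 74% | 7.6% |

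Power to find any pair is identical (66% at 0.6 SD), because both methods start by comparing the smallest p-value with 0.0167. The largest disagreement among the settings tried was with means 0.8/0.4/0 SD: power for digital versus face-to-face is 21 vs 27%, and the declared pairs differ in 11.7% of trials.

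**5. The unnamed test.** With SDs 0.7/1.4/1.4 and the low-SD arm shifted by 0.6, 1.0 or 5, Holm on pooled t has family-wise error 5.2, 7.2 and 9.0%, against 2.6, 3.9 and 4.9% for Holm on Welch t. The pooled figures assume that ANOVA is always used, whereas Section 14 uses it only when its assumptions hold. With a Brown-Forsythe check at .05 (assumed, since the plan names no check), about 94% of such trials leave the ANOVA branch. Pooled-Holm errors inside that branch then occur in 0.4 to 0.7% of all trials.

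**The case for a change.** The strongest case for a change is that it costs almost nothing. Naming Holm and one test per branch is a wording edit within what the plan already allows, and it would deliver the prespecification that the SAP's opening claims. The facts behind this stand: the adjustment is open, no pairwise test is named, Section 19 leaves the software open so no default settles it, and the pairs carry the trial's questions.

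The argument about post hoc choice does not extend to the choice of test. A pooled and a Welch p-value are different numbers, and choosing between them after the fact is not covered by step 3. Among the few trials in step 5 that pass the check, error is still 6 to 11%, and at SDs 0.8/1.2/1.2 about half pass. That is a fair reason to prefer Welch tests. It rests, however, on SDs that the documents do not give.

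The remedy is also less clear-cut than it looks:

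- **Dominance holds only on the same p-values.** Holm on Welch p-values declares fewer pairs than Bonferroni on pooled p-values in 2.2% of trials at 0.6 SD with equal SDs, and in about 8% with SDs 1/1/1.5.
- **The rank branch has its own weakness.** Holm on Mann-Whitney tests, with one distant arm and equal centres in the other two, gave 5.8% error (SDs 0.7 and 1.4) and 6.7% (0.5 and 1.5). Switching to Brunner-Munzel when spreads look different would bring in a new choice made on the data.
- **Dominance does not stop at Holm.** With three arms, Shaffer's multipliers 3, 1, 1 dominate Holm's 3, 2, 1 (power to show both at 0.6 SD: 50 vs 40%). Settling on Holm is a preference.
- **Bonferroni has one advantage.** It comes with matching intervals at 1 − 0.05/3 = 98.3%. At 0.6 SD, a pair significant by Holm has such an interval including zero in 7.3% of trials.
- **Timing cuts both ways.** If outcomes have been seen, naming the more liberal permitted method now would itself be post hoc.

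**Conclusion.** No change to the plan is needed. The open wording is missing detail: an analyst who follows Sections 14 and 18 must adjust, must control the family-wise error, and has two methods to hand that both do so. Moving between those two after seeing the results cannot push the error above 0.05 when the pairwise p-values are valid. What is left is 2 to 3 points of power per pair and 3 to 6 points for showing both peer arms better, under assumed effects of 0.4 to 0.8 SD, normal data, equal SDs and 33 per arm, with no gain in finding any pair.

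The missing test name is filled sensibly by matching the test to the branch: t tests after ANOVA, preferably Welch, and two-arm rank tests after Kruskal-Wallis, read as tests of equal distributions. The inflation figures for pooled tests are scenarios that leave out the plan's assumption check, not estimates for this trial. A sponsor who wishes to tighten the text could name Holm and one test per branch, but sound conclusions do not depend on it. If outcomes were already known when the adjustment was chosen, the results report should show both adjustments and say when the choice was made. This conclusion covers pairs within one endpoint; it does not address multiplicity across endpoints or the non-inferiority question in Section 2.

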## 19. Statistical Software

Analyses will be performed using standard statistical software (e.g., SPSS, R, or Python).

## 20. Administrative Information

Sponsor/Institution: [University / Faculty of Medicine]. Study officials and contacts are listed in the trial registry record. This public document does not include participant names or personally identifiable information.

Any deviations from this plan will be documented in the results submission. This version supersedes prior versions as of the Document Date.
